### **7.2 Definitions of analysis sets**

#### **7.2.1 Efficacy analysis set**

All the patients complete the study per protocol.

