### **3.7 Discontinuation of the study**

Those patients who had not symptom relief after four weeks of esomeprazole would discontinue this study.

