## **4. STUDY PLAN AND TIMING OF PROCEDURES**

The study includes screening and treatment period. The screen period would be 7 days, during this stage all the procedure including questionnaires, upper endoscopy and MII-pH monitoring need to be finished. The treatment period would be 4 to 8 weeks according to the findings under upper endoscopy. For patients with esophagitis, this period would be 8 weeks; for patients with normal findings, this period would be 4 weeks.

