**Table 1 Study Plan detailing the procedures for patients with esophagitis**

Visit	1	2	3	4	5	6	7
Visit window	Screening						
Days -7 to 0 for Visit 1							
±0 day for Visit 2							
±1 day for Visits 3 and 4							
±5 days starting at Visit 5							
Week		0	1	2	4	8	12
Day	-	0	7	14	28	56	84
Written informed consent (including tissue samples, pharmacogenetics)	X						
Demographics	X						
Physical examination, height, and weight	X						
Medical/surgical history	X						
Inclusion/exclusion criteria	X	X					
Treatment dispensed/returned		X					X
Concomitant medication	X	X	X	X	X	X	X
GERD questionnaire		X	X	X	X	X	X

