**Table 2 Study Plan detailing the procedures for endoscopy negative patients**

Visit	1	2	3	4	5	6
Visit window	Screening					
Days -7 to 0 for Visit 1						
±0 day for Visit 2						
±1 day for Visits 3 and 4						
±5 days starting at Visit 5						
Week		0	1	2	4	8
Day	-	0	7	14	28	56
Written informed consent (including tissue samples, pharmacogenetics)	X					
Demographics	X					
Physical examination, height, and weight	X					
Medical/surgical history	X					
Inclusion/exclusion criteria	X	X				
Treatment dispensed/returned		X				
Concomitant medication	X	X	X	X	X	X
GERD questionnaire		X	X	X	X	X

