## **7. STATISTICAL ANALYSES**

### **7.1 Sample size estimate**

Assuming the prevalence of GERD is 30%, 400 completed patients provides a precision (half width of 95% CI) of 0.045 for the estimate of two-sided 95% confidence interval of the primary endpoint..

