### **7.3 Outcome measures for analyses**

Pathologic esophageal acid reflux was defined as the percentage total time for which a pH value < 4 was >4.2 % in the distal esophagus. Then, patients were treated with esomeprazole 20 mg twice daily for 28 days. The symptom scores were measured by the frequency score multiplied by the severity scores of the predominant symptom before and at the end of the treatment, and the “ PPI test ” was defined as positive if the overall scores of the predominant dyspeptic symptom in the fourth week decreased by >50 % compared with those of the baseline. GERD is defined by 24-hour impedance-pH monitoring, upper endoscopy or positive PPI test.

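### The only analysis set is study completers, yet patients without relief at week 4 leave the study; unless that exit counts as completion, PPI-test sensitivity is biased upward

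*Combined protocol and SAP*

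**What the plan says.** Section 7.2.1 gives the only analysis set in one line: "All the patients complete the study per protocol". No set of all enrolled, all treated or all tested patients is defined.

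Section 3.7 reads: "Those patients who had not symptom relief after four weeks of esomeprazole would discontinue this study". Section 7.3 calls the PPI test positive if the score of the predominant symptom "in the fourth week decreased by >50 % compared with those of the baseline". The sensitivity and specificity of that test are the outcome of secondary objective 3 (Synopsis, Objectives; section 2.2). Section 7.4.2 measures them against pH monitoring or endoscopy.

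The study does not end at week 4 for everyone. Section 4 gives patients with esophagitis eight weeks of treatment, and "for patients with normal findings, this period would be 4 weeks". Section 4.3 adds four weeks of follow-up. Table 1 (esophagitis) schedules visits to week 12 and Table 2 (endoscopy negative) to week 8. Both tables include a questionnaire at week 4. Of the seven-day screening period, section 4 says that "during this stage all the procedure including questionnaires, upper endoscopy and MII-pH monitoring need to be finished".

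**The concern.** In a diagnostic accuracy analysis, the result of the index test should not decide who is analysed. Here it may. A patient without relief at week 4 cannot, on the ordinary meaning of the word, have had a fall of more than 50%, so section 3.7 removes PPI-test negatives and leaves PPI-test positives. If those who leave are not completers, section 7.2.1 then drops them from the analysis. Among reference-positive patients, false negatives are lost and true positives are kept, so the observed sensitivity exceeds the true one.

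At stake is secondary objective 3, the diagnostic value of a PPI trial in patients with atypical symptoms. An inflated sensitivity would make the trial look better at detecting reflux disease than it is.

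**Working it through.** **1. The plan's own figure.** Section 7.1 states a half-width of 0.045 for 30% in 400 patients. The check is 1.96 × √(0.30 × 0.70 / 400) = 0.0449, so the figure reproduces. It concerns a proportion among all 400 and is not affected by this point.

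**2. Who is exposed.** The text does not define completion, and three readings are open.

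- *Broad.* The study ends at the last visit in Tables 1 and 2. Every patient who leaves at week 4 is then a non-completer.
- *Narrow.* Section 4 opens by naming only screening and treatment. Endoscopy-negative patients then finish at week 4, and only esophagitis patients, with four weeks of treatment still to go, can be lost. Taking esophagitis as a positive endoscopy, they are reference-positive, so any of them who are PPI-test negative are false negatives.
- *Exit counts as completion.* Nobody is lost and there is no bias.

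**3. Direction and size of the bias.** Let s be the true sensitivity and l the share of reference-positive PPI-test negatives who are lost. Test positives are not removed by section 3.7, so

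observed sensitivity = s / [s + (1 − l)(1 − s)].

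This equals s when l = 0 and exceeds s for any l above 0 if s is below 1. The documents give neither s nor l, so both are assumed below.

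| True s | l = 0.25 | l = 0.50 |
|---|---|---|
| 0.60 | 0.60/0.900 = 0.667 | 0.60/0.800 = 0.750 |
| 0.70 | 0.70/0.925 = 0.757 | 0.70/0.850 = 0.824 |
| 0.80 | 0.80/0.950 = 0.842 | 0.80/0.900 = 0.889 |

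**4. Narrow reading.** Here l is the share of reference-positive test negatives who have esophagitis, multiplied by the share of those who are lost. With a quarter and a half (both assumed), l = 0.25 × 0.5 = 0.125, and s = 0.70 reads 0.70 / (0.70 + 0.875 × 0.30) = 0.70/0.9625 = 0.727. The 0.824 in the table would need half of these test negatives to have esophagitis and every one of them to be lost.

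**5. Is the loss avoidable?** The reference tests are finished in screening, and week 4 is a scheduled questionnaire visit in both tables. A patient who leaves for lack of relief after four weeks should therefore already have both results.

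**The case against.** The strongest reply is that the plan means these patients to count. Someone who leaves under section 3.7 has followed the protocol. Section 3.6 treats withdrawal, including failure to finish esomeprazole, separately from the discontinuation in 3.7. An endoscopy-negative non-responder has finished the four-week course and has a score. Section 7.1 leans the same way: it speaks of "Assuming the prevalence of GERD is 30%, 400 completed patients". If 30% is the share among completers, then 0.70 × 400 = 280 completers do not meet the composite definition of GERD, and any of them who took the PPI test must be negative. Most non-responders would then have to stay in. The flow chart in section 1.3 could not be read for this review and may also show where patients exit.

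This stands as far as it goes: a reading without bias exists and has some support. But no available text states it. The 30% may describe the clinic population before losses instead of the completers, so it cannot settle the matter. The argument about a finished four-week course does not cover esophagitis patients.

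A second reply is that lack of relief is narrower than failing the >50% rule. This stands in full. Patients with partial relief may remain as test negatives, and the share lost could be small.

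A reader might go further and infer that sensitivity is driven to 100%. That needs every reference-positive test negative to be lost, which the documents do not say. A reader might also infer that the GERD share or the primary symptom percentages are materially distorted. That would need response rates by symptom and by diagnosis, and loss rates, none of which the documents give, so no size is claimed.

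**Conclusion.** The concern holds conditionally. If a week-4 exit under section 3.7 is not completion, the analysis set selects on the result of the test being evaluated, and PPI-test sensitivity is biased upward. The direction follows from the two rules, with relief taken in its ordinary sense so that a fall of more than 50% counts as relief. If the exit is completion, there is no effect.

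The size is unknown. The figure of 0.76 to 0.82 for a true 0.70 rests on an assumed loss of a quarter to a half of the reference-positive test negatives. It illustrates the mechanism and is not an estimate.

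A fall in specificity might also be inferred, through loss of true negatives. That cannot be claimed until the population is settled: section 7.4.2 confines the ROC analysis to GERD patients, whereas the Synopsis and section 2.2 refer to patients with atypical symptoms. Who is treated and tested also differs between the Synopsis (Statistical methods) and sections 1.2, 3.4, 4 and 7.3. Both conflicts are separate points to be reconciled.

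The point is worth fixing before analysis, because the rule as written can distort a stated objective and is easily changed.

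**What to change.** For PPI-test accuracy, replace the completer set in section 7.2.1 with all patients with atypical symptoms who started esomeprazole and have a reference-test result. Classify them by the week-4 score under the existing >50% rule, and state that patients discontinued under section 3.7 are included. For patients without a week-4 score, for example those withdrawn earlier under section 3.6, report results with all counted as negative and then with all counted as positive. Define completion, and keep completers as a sensitivity analysis. The clinical discontinuation rule stays as it is. The conflicts over who is treated and tested, and over the ROC population, have to be reconciled for the new set to be well defined.

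No extra visit or test is needed. The sponsor should confirm that the questionnaire listed in Tables 1 and 2 records the frequency and severity scores, which the tables do not say.

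The cost is a little more analysis work and bounds that widen with missing scores. The interval for sensitivity is as wide as the share m of reference-positive patients without a score. With 0.70 among those observed, it runs from 0.70(1 − m) to 0.70(1 − m) + m:

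- m = 5%: 0.665 to 0.715
- m = 15%: 0.595 to 0.745

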### **7.3 Outcome measures for analyses**

Pathologic esophageal acid reflux was defined as the percentage total time for which a pH value < 4 was >4.2 % in the distal esophagus. Then, patients were treated with esomeprazole 20 mg twice daily for 28 days. The symptom scores were measured by the frequency score multiplied by the severity scores of the predominant symptom before and at the end of the treatment, and the “ PPI test ” was defined as positive if the overall scores of the predominant dyspeptic symptom in the fourth week decreased by >50 % compared with those of the baseline. GERD is defined by 24-hour impedance-pH monitoring, upper endoscopy or positive PPI test.

### **7.4 Methods for statistical analyses**

#### **7.4.1 Analysis of the primary variable(s)**

The percentage of each symptom of GERD in the symptom questionnaire in Chinese outpatients in Gastroenterology department will be calculated. The symptom of the highest percentage will be the primary symptom.

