### **Statistical methods**

Assuming the prevalence of GERD is 30%, 400 completed patients provides a precision (half width of 95% CI) of 0.045 for the estimate of two-sided 95% confidence interval of the primary endpoint. All patients underwent upper endoscopy or an ambulatory 24-h pH monitoring. Pathologic esophageal acid reflux was defined as the percentage total time for which a pH value < 4 was >4.2 % in the distal esophagus. Then, patients were treated with esomeprazole 20 mg twice daily for 28 days. The symptom scores were measured by the frequency score multiplied by the severity scores of the predominant symptom before and at the end of the treatment, and the “ PPI test ” was defined as positive if the overall scores of the predominant dyspeptic symptom in the fourth week decreased by >50 % compared with those of the baseline.

Clinical Study Protocol  
Drug Substance Esomeprazole  
Study Code D9612L00157  
Edition 2.0  
Date Jun 8 2018

GERD is defined by either 24-hour impedance-pH monitoring or positive PPI test or positive result from endoscopy. The percentage of each symptom of GERD in the symptom questionnaire in Chinese outpatients in Gastroenterology department will be calculated. The symptom of the highest percentage will be the primary symptom.

	PAGE
TITLE PAGE .....	1
PROTOCOL SYNOPSIS.....	2
TABLE OF CONTENTS.....	5
1. INTRODUCTION .....	7
1.1 Background and rationale for conducting this study .....	7
1.2 Rationale for study design, doses and control groups.....	8
1.3 Study Design .....	9
2. STUDY OBJECTIVES.....	10
2.1 Primary objective .....	10
2.2 Secondary objectives.....	10
2.3 Safety objectives .....	10
3. SUBJECT SELECTION, ENROLMENT, RANDOMISATION, RESTRICTIONS, DISCONTINUATION AND WITHDRAWAL.....	10
3.1 Inclusion criteria .....	11
3.2 Exclusion criteria .....	11
3.3 Subject enrolment and randomization.....	11
3.4 Methods for assigning treatment groups .....	11
3.5 Methods for ensuring blinding.....	11
3.6 Criteria for withdrawal.....	12
3.7 Discontinuation of the study .....	12
4. STUDY PLAN AND TIMING OF PROCEDURES.....	12
4.1 Enrolment/screening period .....	15
4.2 Treatment period.....	15
4.3 Follow-up period.....	15
5. SAFETY REPORTING AND MEDICAL MANAGEMENT .....	15
5.1 Definition.....	15
Adverse Events.....	15
Serious Adverse Event.....	15
Adverse Drug Reaction (ADR) .....	16

5.2	Reporting of Serious Adverse Events.....	16

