heartburn symptoms would underestimate the prevalence of GERD. The last and also the most important reason might lie in that the symptoms which indicate reflux were different in Chinese population. In other words, heartburn might not be the primary reflux symptom in China. For example, more symptoms originated from the upper gastrointestinal tract was described as reflux symptom when patients went to see doctors in China. According to the investigation in our own center, about one third of dyspepsia patients without reflux symptoms presented pathologic esophageal acid reflux in our clinic. Thus heartburn was not understood as well as in other western countries, the symptoms of GERD might distribute differently in China compared to other western countries. So it is necessary to investigate the primary symptoms and spectrum of GERD in Chinese population in order to better define and diagnose GERD.

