### **3.1 Inclusion criteria**

1. Consecutive patients aged 18–65 years who go to the gastroenterology clinic presented with upper gastrointestinal discomfort, such as the following symptoms: heartburn, regurgitation, dysphagia, substernal pain, epigastric pain, epigastric burning, early satiety, postprandial fullness.
2. The previous symptoms should last for at least 3 months.
3. The frequency of the previous symptoms should be at least 3 days per week with at least moderate.
4. All the previous symptoms would be evaluated in the questionnaires (see attachment).

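### The primary symptom is picked on the highest raw percentage with no measure of uncertainty or tie rule, and the 0.045 precision in 7.1 belongs to GERD prevalence, not to this ranking

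*Combined protocol and SAP*

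**What the plan says.** The only primary objective (synopsis and section 2.1) is to establish which symptom is the primary one in GERD. Section 7.4.1 gives the whole primary analysis in two sentences, which the synopsis repeats under Statistical methods: "The percentage of each symptom of GERD in the symptom questionnaire in Chinese outpatients in Gastroenterology department will be calculated", and then "The symptom of the highest percentage will be the primary symptom". Section 7.4.2 lists the same percentages again as a secondary analysis and adds nothing on uncertainty.

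Section 3.1 names eight candidate symptoms, as examples: "heartburn, regurgitation, dysphagia, substernal pain, epigastric pain, epigastric burning, early satiety, postprandial fullness".

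Section 7.1 bases the sample size on one input: "Assuming the prevalence of GERD is 30%, 400 completed patients provides a precision (half width of 95% CI) of 0.045". It attaches that precision to the primary endpoint.

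The synopsis sets out who counts as a GERD patient: "GERD is defined by either 24-hour impedance-pH monitoring or positive PPI test or positive result from endoscopy". Section 7.3 uses the same composite.

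**The concern.** The rule takes the largest of at least eight estimated percentages and names it, whether it leads by 20 points or by one patient. Nothing tells the reader how secure the order is, and nothing says what happens if two symptoms tie.

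Section 7.1 then appears to supply the missing precision, but its input is the prevalence of GERD among all patients. Prevalence is neither a primary nor a secondary outcome. The plan therefore states no precision for its actual primary endpoint, and the figure it does state is more favourable than that endpoint can have.

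This matters because the named symptom is the headline. Section 1.1 motivates the study with the idea that "heartburn might not be the primary reflux symptom in China". A result that displaces or confirms heartburn on a lead compatible with chance would be read as an answer to that question. The percentages will be reported, so a small lead would be visible, but the uncertainty of the order would not be.

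**Working it through.** **Inputs from the documents.** GERD prevalence 0.30, 400 completed patients, two-sided 95% CI (section 7.1); eight named symptoms (section 3.1); composite GERD definition (synopsis and section 7.3).

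**1. Reproduce the plan's figure.** Half-width = 1.96 × √(p(1 − p)/n). With p = 0.30 and n = 400 this is 1.96 × √(0.21/400) = 0.0449, which rounds to 0.045. The arithmetic is right, but for prevalence among all 400 patients.

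**2. Denominator of the primary endpoint.** Section 7.4.1 does not state it. The natural reading is GERD patients, so the plan's own assumption gives 0.30 × 400 = 120. The number could be higher. The composite includes PPI responders, and the centre's own experience, "about one third of dyspepsia patients without reflux symptoms presented pathologic esophageal acid reflux in our clinic", concerns patients without reflux symptoms only. The range 120 to 400 is therefore carried through.

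**3. Half-widths for the quantities the rule uses.**

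- One symptom, n = 120: at 30%, 1.96 × √(0.21/120) = 0.082; at 50%, 1.96 × √(0.25/120) = 0.089.
- Difference between two uncorrelated symptoms near 50%, n = 120: 1.96 × √(0.50/120) = 0.127.

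| n | one symptom at 50% | difference, uncorrelated |
|---|---|---|
| 120 | 0.089 | 0.127 |
| 200 | 0.069 | 0.098 |
| 300 | 0.057 | 0.080 |
| 400 | 0.049 | 0.069 |

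Positive correlation between symptoms narrows the difference. For 50% against 45% at n = 120, its half-width is 0.126, 0.106 and 0.089 at correlations 0, 0.3 and 0.5. If each patient counted under one symptom only, it would be wider: for 30% against 25% at n = 120, 1.96 × √((0.55 − 0.05²)/120) = 0.132.

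**4. How often the rule names the wrong symptom.** The documents give no symptom percentages, so this step rests on assumed ones. The base list is 50/45/42/40/35/30/20/10%, with the leader raised to 55% or 60% in the alternatives. Symptoms are independent binomials, ties are broken at random, and there are 400,000 runs per scenario.

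| true leader (lead) | n = 120 | n = 200 | n = 300 | n = 400 |
|---|---|---|---|---|
| 50% (5 points) | 28.6% | 19.2% | 12.5% | 8.5% |
| 55% (10 points) | 8.0% | 2.7% | 0.8% | 0.2% |
| 60% (15 points) | 1.2% | 0.1% | 0.01% | <0.01% |

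In the 5-point list, symptoms tie for first in 5.7% of runs at n = 120 and 1.2% at n = 400.

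**5. Sensitivity to independence.** With a latent correlation of 0.3 or 0.5 between symptoms, the error in the 5-point list falls to about 25% or 21% at n = 120, and to about 15% or 13% at n = 200.

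**The case against.** The strongest reply is that this is a descriptive definition in a single-site cross-sectional survey. Primary simply means most frequent, every percentage is shown, and a reader can work out single-symptom intervals from the percentage and n. Section 7.1 does mention a 95% interval for the primary endpoint, and the outcome measure speaks of symptoms in the plural, which leaves room for joint leaders. The questionnaire is an attachment outside the text and may say more.

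The misranking rates also depend on invented percentages. With a 15-point lead the problem almost vanishes, and correlation reduces it. The 29% counts every swap as an error, including swaps between two symptoms other than heartburn. In the same list at n = 120, a heartburn that is truly second, third or fourth is wrongly named first in about 19%, 7% or 3% of runs. Finally, 120 may be too low: section 3.7 discontinues patients without relief and section 7.2.1 analyses completers, which could raise the GERD share.

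Several of these points stand as limits on size. The risk is material only when the true lead is about 5 points or less, or the GERD group is small. If the question is only about heartburn, the 29% is an upper figure unless heartburn is the true leader. None of them removes the defect. The interval in 7.1 is the misattributed one, and a plural noun is not a tie rule. The interval for the lead needs patient-level data, so readers cannot recover it from published percentages. A larger GERD group moves n within the range already shown. Even at 400, the half-width for the difference between two uncorrelated symptoms near 50% is 0.069, not 0.045.

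**Conclusion.** The concern holds. The 0.045 in section 7.1 is correct for a 30% prevalence in 400 patients and wrong as the precision of the primary endpoint. On the natural denominator and the plan's own 30%, the half-width for a symptom at 30% to 50% is 0.082 to 0.089, about twice the stated figure, and the half-width for an uncorrelated lead near 50% is about 0.13. These values depend on the size of the GERD group and fall to 0.049 (a symptom at 50%) and 0.069 (the lead) if all 400 patients qualify.

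The chance of naming the wrong symptom cannot be fixed from the documents. Under the assumed independent list it runs from 29% (5-point lead, n = 120) to well under 1% (15-point lead, n = 200 or more). The plan should be changed, because the headline is affected and the remedy is cheap. Neither the design nor the ranking itself is invalidated.

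**What to change.** Keep the frequency ranking, the sample size and the data collection, and change the following.

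- **Section 7.1 and synopsis:** say that 0.045 refers to GERD prevalence in 400 patients. Add the expected half-width for a symptom percentage among the expected number of GERD patients: about 0.09 at 120, falling to about 0.05 at 400.
- **Section 7.4.1 and synopsis:** state that the denominator is GERD patients. Report (a) each symptom's percentage with a 95% CI, (b) a paired 95% CI for the lead of the top symptom over the runner-up, and (c) the bootstrap probability, resampling patients, that each symptom ranks first. Read all three descriptively, because the leader is chosen from the same data.
- **Ties:** report tied symptoms jointly.
- **Headline:** give the named symptom together with its lead CI and rank probability.

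The label should not depend on whether the lead CI excludes 0, because that criterion is too conservative. At n = 120, with leads of 5, 10 and 15 points in the assumed lists:

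| lead | ranking correct | lead CI excludes 0 | median bootstrap probability that the observed leader ranks first |
|---|---|---|---|
| 5 points | 71% | 5% | 0.68 |
| 10 points | 92% | 23% | 0.86 |
| 15 points | 99% | 56% | 0.97 |

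The cost is a few sentences in the plan and a little more analysis of data already being collected. The downside is a less favourable stated precision and a less firm headline when the lead is small.

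### The primary-symptom rule ranks frequency within GERD patients and never compares them with the non-GERD patients enrolled, so it cannot show which symptoms indicate GERD

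*Combined protocol and SAP*

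**What the plan says.** Section 7.4.1 gives the whole primary analysis in two sentences: "The percentage of each symptom of GERD in the symptom questionnaire in Chinese outpatients in Gastroenterology department will be calculated", and then "The symptom of the highest percentage will be the primary symptom". The statistical methods paragraph of the synopsis says the same. The denominator is not spelled out; the natural reading is patients classified as GERD, which section 7.3 defines as a positive result on any of pH monitoring, endoscopy or the PPI test.

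The cohort is wider than that. Section 3.1 enrols consecutive patients "who go to the gastroenterology clinic presented with upper gastrointestinal discomfort" and lists eight example symptoms, several of them dyspeptic. Section 7.1 plans for 400 completers and assumes that 30% have GERD, so most of the cohort is expected not to have it.

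In section 7.4.2 the first secondary analysis repeats the same percentages. The ROC analysis there concerns GERD Q and the PPI test, not individual symptoms. Section 7.2.1 limits the analysis set to patients who complete per protocol, and section 3.7 takes patients without relief at four weeks out of the study.

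**The concern.** Everyone enters with an upper GI complaint, with or without GERD. A complaint that is common among all attenders will therefore be common among the GERD patients too, even if it has no association with reflux. Such a symptom can come first and be reported as the primary symptom of GERD.

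Section 1.1 asks which symptoms indicate reflux in Chinese patients and wants the answer to improve definition and diagnosis. Those are questions about association, and frequency among cases alone does not answer them. At stake is how the study's only primary result is read: a dyspeptic symptom could top the list through case mix and be taken as a diagnostic pointer.

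**Working it through.** **Inputs.** From section 7.1: n = 400, GERD prevalence 30%, two-sided 95% confidence. The symptom rates below are assumptions, because the documents give none.

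**1. The plan's own figure.** Section 7.1 says "400 completed patients provides a precision (half width of 95% CI) of 0.045". The Wald half-width is 1.96 × √(0.30 × 0.70 / 400) = 0.0449, so it reproduces. It is the precision of GERD prevalence in all 400 patients. A symptom percentage among the GERD patients alone (400 × 0.30 = 120) has a half-width of 1.96 × √(0.30 × 0.70 / 120) = 0.082 at a rate of 30%, or 1.96 × √(0.50 × 0.50 / 120) = 0.089 at 50%.

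**2. Group sizes.** 120 GERD and 400 − 120 = 280 non-GERD.

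**3. Illustration (assumed rates).**

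| Symptom | GERD | Non-GERD | Likelihood ratio | Probability of GERD given the symptom |
|---|---|---|---|---|
| Fullness | 60% | 60% | 0.60/0.60 = 1.0 | 0.18/(0.18 + 0.42) = 0.30 |
| Regurgitation | 45% | 15% | 0.45/0.15 = 3.0 | 0.135/(0.135 + 0.105) = 0.56 |

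Fullness leaves the probability of GERD at its starting 30%, yet the rule ranks it first.

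**4. How often the rule does this.** Independent binomial draws for the two symptoms in 120 GERD patients, 20,000 simulated studies, fullness at 60%:

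| Regurgitation rate in GERD | Fullness ranked ahead |
|---|---|
| 45% | about 99% |
| 50% | about 93% |
| 55% | about 76% |

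**5. Can the cohort support the comparison?** For regurgitation, the 95% half-width of the difference is 1.96 × √(0.45 × 0.55/120 + 0.15 × 0.85/280) = 0.098. For a symptom near 50% in both groups it is 1.96 × √(0.25/120 + 0.25/280) = 0.107. If GERD prevalence were 20%, 50% or 60%, that last figure would be 0.122, 0.098 or 0.100. With 120 against 280, the difference detectable with 80% power at two-sided 0.05 is 13 to 15 percentage points for non-GERD rates of 20% to 60%. With Bonferroni adjustment over the eight listed symptoms it is 17 to 19 points. The assumed 45% against 15% contrast would be detected with power above 99% even at 0.05/8.

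**6. Condition on step 5.** These figures need both groups to be retained. Non-GERD patients are PPI-test negative by definition, so they are the group most exposed to discontinuation under section 3.7 and exclusion under section 7.2.1. The non-GERD group could end up both smaller and selected.

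**The case against.** The strongest reply is that the objective is descriptive. Sections 2.1 and 2.2 speak of defining the primary symptom and of symptom distribution, and sections 1.1 and 1.2 speak of a spectrum. On that reading, frequency within GERD is the estimand and the rule answers it; better diagnosis is a later motive and not an endpoint. This largely stands. A reader might infer that the primary analysis is invalid or confounded, but the documents do not support that: the percentage among GERD patients in this clinic is a legitimate description of the named population. Section 1.1 suggests only that heartburn might not be the leading reflux symptom in China. What remains is that the same section also speaks of symptoms that indicate reflux, so the objective is ambiguous and the label invites the diagnostic reading.

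A reader might also set the background statement that "about one third of dyspepsia patients without reflux symptoms presented pathologic esophageal acid reflux in our clinic" beside the 30% in section 7.1 and conclude that dyspeptic symptoms carry almost no information about GERD. That does not follow. The first figure is acid reflux in dyspepsia patients without reflux symptoms. The second is a planning assumption, with no source given, for GERD under a broader three-test definition. Populations and definitions differ.

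Two further objections also stand. The illustration shows that the rule can mislead, not how likely that is here. And a simple GERD against non-GERD contrast would partly measure which symptoms respond to a PPI, because a positive PPI test alone classifies a patient as GERD and is judged on change in the predominant symptom.

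**Conclusion.** The point holds as a limit on interpretation and should be fixed. As written, section 7.4.1 yields a valid ranking of symptoms within GERD, but it cannot support a statement that the top symptom indicates or helps to diagnose GERD. Under the assumed rates, an uninformative symptom is ranked ahead of one with a likelihood ratio of 3.0 or more in about 76% to 99% of simulated studies. Those percentages depend on invented rates and a two-symptom comparison. The precision of about 0.10 for a difference rests on 30% prevalence and on keeping all 120 and 280 patients, which the current analysis set does not secure.

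**What to change.** In section 7.4.1 and the synopsis:

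- Keep the ranking as a descriptive result and state its denominator.
- Tabulate each symptom's baseline percentage in GERD and non-GERD patients, with the difference or likelihood ratio and its 95% CI.
- Describe the top symptom as a marker of GERD only if the CI for its difference, adjusted for the number of symptoms ranked, lies above zero. Otherwise call it the most common presenting complaint among GERD patients.
- Run this comparison in all enrolled patients with a baseline questionnaire and a diagnostic classification, not only per-protocol completers. Reconcile sections 3.7 and 7.2.1 so that it is clear how patients without relief are counted.
- Repeat the table with GERD defined by pH monitoring or endoscopy alone.

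The cost is a separate analysis set for this table, extra columns, one sensitivity table and possibly a more cautious headline. The questionnaire and diagnostic tests are already planned, so no new patients or procedures are needed.
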